1.4.2 Secondary Endpoint(s)

To assess the safety of removal of antiplatelets from the antithrombotic regimen, non-surgical major hemorrhagic events, non-surgical major thrombotic events, bleeding, stroke, pump thrombosis and survival will be compared between the two arms of the study.

1.4.3 Descriptive Endpoint(s)

This study will also assess changes in the Hemocompatibility Score, Rehospitalization, and Economic Cost Implications as a result of removal of antiplatelets from the antithrombotic regimen.

1.5 Randomization

1.6 Blinding

This is a double-blind study, neither patient nor investigator will know the subject's randomization throughout the study follow up. Additionally, sponsor personnel and the CEC will not have access to patient or population blinding information. The blind of the study will only be broken once the study follow-up is completed, and adverse event adjudication is completed. Questions related to unblinding should be directed to the Sponsor.

Statistical Analysis Plan

2.2 Statistical Methods

2.2.1 Descriptive Statistics for Continuous Variables

Continuous variables will be summarized with the numbers of observations, means and standard deviations, with quartiles, minimum and maximum.

2.2.2 Descriptive Statistics for Categorical Variables

Categorical variables will be summarized with subject counts and percentages/rates, and with exact 95% Clopper-Pearson confidence intervals.

2.3 Endpoint Analysis

2.3.1 Primary Endpoint

The primary endpoint is a composite of survival free of any non-surgical¹ major hemocompatibility related adverse event² at 1-year post implant.

¹ - Non-surgical – any event occurring > 14-days post implant.

² - Major Hemocompatibility Related Adverse Event:

- Stroke
- Pump Thrombosis (suspected or confirmed)
- Bleeding (including intracranial bleeds that do not meet the stroke definition)
- Arterial Peripheral Thromboembolism

A subject will be considered a success if they survive to their 12 month visit and have not experienced a non-surgical hemocompatibility related adverse events. Subjects who have an outcome (e.g. transplanted or explanted due to recovery) prior to their 12 month visit that have not reported a non-surgical hemocompatibility related adverse event prior to censoring will also be considered a success.

A subject will be considered a failure if:

- the subject expires prior to their 12 month visit
- the subject experiences a non-surgical hemocompatibility related adverse event prior to their 12 month visit.

The primary analysis will be performed using the mITT population.

[REDACTED]

[REDACTED]

[REDACTED]

[REDACTED]

Statistical Analysis Plan

2.3.1.2 Sample Size

[REDACTED]

2.3.1.3 Analysis Methods

[REDACTED]

2.3.1.4 Justification of the Non-Inferiority Margin

[REDACTED]

2.3.1.5 Poolability Analysis

[REDACTED]

Statistical Analysis Plan

A large black rectangular redaction box covers the majority of the page content, starting below the header and ending above the footer. The redaction is irregular, with some jagged edges and varying thicknesses, suggesting it was created by a digital tool rather than a physical redaction.

Statistical Analysis Plan

[REDACTED]

[REDACTED]

[REDACTED]

[REDACTED]

[REDACTED]

[REDACTED]

2.3.2 Secondary Endpoints

The secondary endpoints will be analyzed using the mITT population.

Non-surgical Major Hemorrhagic events: Hemorrhagic event rate per patient year will be calculated by dividing all non-surgical bleeding events and hemorrhagic stroke events by the cumulative years of study exposure. This rate will be compared between groups using Poisson regression.

Non-surgical Major Thrombotic events: The thrombotic event rate per patient year will be calculated by dividing the number of non-surgical ischemic strokes, pump thrombosis and arterial peripheral thromboembolic events by the cumulative years of study exposure. This rate will be compared between groups using Poisson regression.

Survival: The overall survival rate will be analyzed using a Kaplan-Meier analysis and the treatment groups compared using the log-rank test. Survival will be calculated starting at 14 days post implant.

Stroke Rate: The stroke rate will be calculated based on the number of strokes experienced by subjects, 14 days or more after device implant, and while on their treatment assignment, divided by the cumulative duration of study exposure (years of support). The treatment groups will be compared by using Poisson regression.

All strokes that occur 14 or more days after implant will be included, regardless of the treatment status of the subject (subjects who move off their randomized treatment will continue to be followed). Ischemic and hemorrhagic stroke rates and debilitating stroke rate (MRS > 3) will also be analyzed. The stroke rate and treatment comparison will be performed as described above.

Time to first non-surgical stroke event will also be analyzed using a Kaplan-Meier analysis. The treatment groups will be compared using a log-rank test.

Statistical Analysis Plan

Pump Thrombosis: The pump thrombosis rate will be calculated based on the number of suspected or confirmed pump thrombosis events experienced by the subject, 14 or more days post device implant, while on their treatment assignment divided by the cumulative duration of study exposure (years of support). The treatment groups will be compared by using Poisson regression.

All suspected pump thrombosis that occurs 14 or more days post implant will be included, regardless of the treatment status of the subject (subjects who move off their randomized treatment will continue to be followed). The pump thrombosis rate and treatment comparison will be performed as described above.

Bleeding: All bleeding events that occur will be captured. Subjects who terminate the study prematurely without experiencing any bleeding will have the time they were in the study counted in the analysis. For the mITT population, bleeding events will be included while the subject remains on their randomization assignment until the last randomized patient has been followed to one year. This will result in some subjects being followed for more than one year.

Bleeding rates will be differentiated based on severity and will include moderate bleeding, severe bleeding and fatal bleeding. Gastrointestinal (GI) bleeding and non-surgical bleeding will also be analyzed. The bleeding rate (events per patient year) will be calculated by dividing the number of bleeding events by the cumulative duration of study exposure (years of support). Bleeding rates will be compared between treatment groups using Poisson regression. In addition, a subgroup analysis will be performed according to subject aspirin responsive testing.

In addition, all secondary endpoints will be analyzed to include non-surgical major hemocompatibility related adverse events beyond the time of transition to open label in the mITT population.

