5.6 Transition to Open Label

During a subject's clinical course, post-randomization events may result in the investigator mandating antiplatelet therapy. The mandate may consist of the presence of an antiplatelet or the absence of all antiplatelets from the patient's antithrombotic regimen in response to clinical events. These subjects should remain in the study for the full 12-month study follow up whenever possible. Investigators may cease administration of the treatment arm medication for up to 72 hours without transitioning the subject to open label. In these instances, the treatment arm medication is no-longer administered, and investigator initiates their mandated therapy. If the cessation extends beyond 72 hours, these subjects are considered to have transitioned to open label and may not resume the treatment arm medication after transition.

Transition to open label does not constitute unblinding. Investigators will not know which randomized treatment arm patients who transition to open label were initially allocated. Study blinding will continue in patients transitioned to open label.

Clinical events which resulted in the transition to open label will be documented in the EDC. Subjects who transition to open label after 12 months will be considered to have completed the study required follow up at 12 months post implant. Subjects who transition to open label after 12-months of study follow up will be considered to have completed study follow up at that time except if a subject has experienced a stroke or potential stroke neurologic adverse event prior to transitioning to open label, then they will be followed for an additional 60-days post event for MRS score evaluation. In this case, the subject is considered to have reached end of study follow up upon completion of the MRS evaluation.

Clinical Investigation Plan

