6.4 Baseline

The baseline assessments in table 3 will be performed.

Table 3 – Baseline Data Collection

Study Activity	Data Collection
Informed Consent	Informed consent details
Inclusion/Exclusion	Subject's eligibility details
Demographics	Age, height, gender, ethnicity (except where prohibited by regulation), race (except where prohibited by regulation), blood type, INTERMACS profile, and NYHA class
General and Cardiac Medical History	Etiology of HF, duration of HF, therapeutic intent (BTT/BTC/DT), arrhythmias, prosthetic valve(s), history of stroke, diabetes, smoking, history of bleeding (diverticular disease, diagnosed arteriovenous malformations (AVMs), GI ulcer(s), anemia and/or erythropoietin treatment), aortic stenosis, hypertension, history of MI, peripheral thromboembolism, coronary stents, CABG, substance abuse (drug/alcohol), drug/radiation toxicity, peripheral vascular disease, carotid artery disease, cardiac rhythm management device, intra-aortic balloon pump, other pre-implant circulatory support, CardioMEMS, and HIV status
Modified Rankin Score	Modified Rankin Score (MRS)
Vital Signs	Weight, blood pressure, and heart rate
Anticoagulation/Antiplatelet Medications	Vitamin K antagonist (e.g. warfarin, fluindione, phenprocoumon, etc.), clopidogrel, dipyridamole, other anticoagulation agents, other vitamin K antagonists, direct thrombin inhibitors, etc. (including treatment arm medication) All new medications started, or current medications stopped during the follow-up period must be recorded. All dose changes (including IV titrations as total daily dose) during the follow-up period must be recorded with the exclusion of vitamin K antagonist. Only the type, start and stop dates, and target INR will be collected for vitamin K antagonist.
Other Medications	ACE inhibitors, inotropes, ARBs, beta blockers, antiarrhythmics, statins, nitrates, allopurinol, aldosterone blockers, antibiotics, diuretics, insulin and antidiabetic medications, and other cardiovascular medications

Clinical Investigation Plan

Study Activity	Data Collection

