1.4 Endpoints

1.4.1 Primary Endpoint

The primary endpoint for this study will be met if the placebo arm is non-inferior to the aspirin arm in the composite of survival free of any non-surgical¹ major hemocompatibility related adverse event² at 1-year post implant.

¹ - Non-surgical – any event occurring > 14-days post implant.

² - Major Hemocompatibility Related Adverse Event:

- Stroke
- Pump Thrombosis (suspected or confirmed)
- Bleeding (including intracranial bleeds that do not meet the stroke definition)
- Arterial Peripheral Thromboembolism

Statistical Analysis Plan

This study assesses the overall change in the overall incidence of major hemocompatibility related adverse events. Additional secondary endpoints will also be evaluated to monitor effects on other study outcome measures.

This composite primary endpoint reflects the interrelatedness of hemocompatibility related adverse events, providing an endpoint that will result in a clear answer to the study's primary question of whether or not anti-platelets are required to maintain the safety and efficacy profile of the HM3. Because post-implant clinical course can be widely variable due to clinical responses to adverse events, this composite endpoint focuses on the first major hemocompatibility related adverse event to ensure the effect of the treatment arm is reflected in the primary endpoint measure. Non-composite endpoints or endpoints that do not focus on the first event have the possibility of being rendered futile or distorted by treatment responses to prior adverse events.

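### Repeat bleeds are compared with Poisson regression and no allowance for within-patient clustering, so nominal p-values are too small if bleeding risk differs between patients

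*SAP*

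**What the plan says.** SAP 2.3.2 (Bleeding) captures all bleeding events, divides their number by cumulative years of support, and says that "Bleeding rates will be compared between treatment groups using Poisson regression". The Non-surgical Major Hemorrhagic rate is built the same way, by "dividing all non-surgical bleeding events and hemorrhagic stroke events by the cumulative years of study exposure", and is also compared by Poisson regression.

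Two counting rules apply. In the mITT population "bleeding events will be included while the subject remains on their randomization assignment". In addition, "all secondary endpoints will be analyzed to include non-surgical major hemocompatibility related adverse events beyond the time of transition to open label".

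For stroke the SAP adds a first-event analysis: "Time to first non-surgical stroke event will also be analyzed using a Kaplan-Meier analysis". It names none for bleeding. SAP 2.8 makes no multiplicity adjustment, and SAP 2.6 ties trial success to the primary endpoint alone.

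**The concern.** These are counts of events, not of patients, and CIP 5.8 allows 12 to 36 months of follow-up, so one patient can add several bleeds. Poisson regression with its default standard errors treats all events as independent, with variance equal to the mean. If patients differ in bleeding risk, the variance exceeds the mean and the standard error is understated.

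Unequal risk is plausible here. CIP Table 3 (section 6.4) records "history of bleeding (diverticular disease, diagnosed arteriovenous malformations (AVMs), GI ulcer(s), anemia and/or erythropoietin treatment", and none of these is by itself an exclusion in CIP 5.3.2. Exclusion 2 does remove patients for whom the investigator mandates no antiplatelet agent.

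At stake is a supportive claim. The CIP 2.2 hypothesis includes a possible reduction in non-surgical bleeding, and these rates are where it would be tested. P-values, and rate-ratio intervals if reported, would look more precise than they are. The estimated rate ratio is not biased by this.

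**Working it through.** The plan states no expected bleeding rate, dispersion or power for these comparisons, so there is no planned figure to reproduce.

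**Inputs from the documents**
- 628 randomized 1:1 (CIP 5.7, 3.0): 314 per arm.
- 24 months of enrolment and 36 in total (CIP 5.8): administrative follow-up uniform over 12-36 months.
- Open label before month 12: followed to month 12, then exit (CIP 5.8, 6.8.1). Later: "Subjects who transition to open label after 12-months of study follow up will be considered to have completed study follow up at that time" (CIP 5.6). The 60-day stroke extension is ignored.
- Bleeding by 2 years of 34% and 43.7% (CIP 1.1.1), read as the share of patients with any bleed. Both cover all bleeding, so they are upper anchors.

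**Assumptions**
- Frailty variance θ from 0 to 2.
- 30% or 60% of on-treatment bleeds lead to open label.
- Other exits at 25% per year.
- Two-sided nominal 5% test; counting starts at day 14.

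**Step 1: rates.** Patient rate = r·z, with z gamma, mean 1 and variance θ. Solve 1 − (1 + 2θr)^(−1/θ) = P. At θ = 1, r = (1/(1 − P) − 1)/2:
- P = 0.34: (1.515 − 1)/2 = 0.258 per patient-year
- P = 0.437: (1.776 − 1)/2 = 0.388 per patient-year

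Over θ = 0 to 2, r runs from 0.21 to 0.54.

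**Step 2: hand check, one full year each.** Var(count) = μ(1 + θμ), so the Poisson variance is too small by the factor 1 + θμ. True error = 2[1 − Φ(1.96/√(1 + θμ))].
- θ = 1, μ = 0.258: factor 1.258, SE ratio 1.12, error about 8%
- θ = 1, μ = 0.388: factor 1.388, SE ratio 1.18, error about 9.6%

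**Step 3: simulation with the exit rules, no true effect, 20,000 trials per cell.** Poisson variance of the log rate ratio: 1/Y₁ + 1/Y₀. Robust variance: Σ(y − rate·t)²/Y² summed over arms. The on-treatment ranges cover exposure stopping at open label or running to study exit.

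| θ | Patients with two or more bleeds | Poisson error, beyond open label | Poisson error, on treatment |
|---|---|---|---|
| 0 | 3-6% | 4.9-5.2% | near 5%; 4.1-4.7% if exposure runs on after counting stops |
| 0.5 | not tabulated | 6.2-7.7% | 4.9-7.3% |
| 1 | 5-12% | 8.1-10.9% | 5.8-10.0% |
| 2 | 8-16% | 12.3-18.7% | 7.3-15.2% |

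Robust errors gave 4.5-5.4% in every bleeding cell. At θ = 1 a correct interval is 12-22% wider beyond open label and 4-19% wider on treatment.

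**Step 4: sensitivity**
- Exits at 10% per year, θ = 1: 8.4-11.6% beyond open label, 5.9-10.5% on treatment.
- Bleeding rate after open label halved or raised by half, θ = 1: 7.0-12.3% beyond open label.
- No bleed ever leads to open label (upper bound), θ = 1: 10.7-13.6%.
- Rarer bleeding categories, assumed 15-25% by 2 years: 4.9-7.6% at θ = 1, 5.6-10.8% at θ = 2.
- Stroke at 10%, θ = 1: 5.1-5.5%. Pump thrombosis at 1.5%: below 1%.

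**The case against.** The strongest reply has four parts.

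- **Patient-level bleeding is already reported.** SAP 2.10 gives one-year adverse events by arm as subjects, events and rates, and SAP 2.2.2 gives exact intervals for categorical data. Clustering does not affect the subject percentages, and events shown beside subjects reveal recurrence. This stands as description. But SAP 2.10 states no between-arm test and stops at one year, so the Poisson comparison remains the only stated test of the bleeding rates.
- **The evidence for dispersion is indirect.** SAP 1.4.1 warns that "endpoints that do not focus on the first event have the possibility of being rendered futile or distorted by treatment responses to prior adverse events", but that concerns therapy changes after an event, which is a matter of bias, not of unequal risk between patients. This is a fair reading, and the point does not rely on that sentence. A list of baseline fields does not yield a variance either.
- **The size is assumed, and can be small.** If 80% of bleeds led to open label, on-treatment error would be 4.7-6.8% at θ = 1, and on-treatment counting is the main rule for bleeding. This stands: at low dispersion or for rarer categories the problem is minor.
- **The consequence is limited and the text may be incomplete.** The p-values are nominal, with no stated alpha, and robust errors would be compatible with the words Poisson regression. CIP section 8 and part of the SAP appendices are redacted. This also stands, but SAP 2.3.2, the natural place for a variance method, is legible and silent.

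**Conclusion.** The point holds, conditionally. As written, the comparisons of the non-surgical, moderate, severe and GI bleeding rates and of the non-surgical major hemorrhagic rate understate their standard errors to the extent that bleeding risk differs between patients. At an assumed frailty variance of 1, true error is roughly 6-11% across both counting rules instead of 5%; at variance 2, roughly 7-19%; at variance 0 there is no inflation. These figures depend on the assumed dispersion, open-label share and exit rate, none of which the documents give.

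The point does not extend to fatal bleeding, which can occur only once per patient, or to pump thrombosis, and it is small for stroke. It is a worthwhile correction to a supportive analysis and no threat to the trial's main conclusion. Confidence is medium because of the redactions and the missing dispersion figure.

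**What to change.** In SAP 2.3.2, for the five rates named above and under both counting rules, replace Poisson regression with *Poisson regression with a log(patient-years) offset and subject-level robust (sandwich) standard errors*, and report rate ratios with 95% confidence intervals. Negative binomial regression with the same offset is an acceptable alternative: its likelihood-ratio test gave 3.8-6.0% error at variances 0, 1 and 2, with 45% of bleeds leading to open label (400 trials per cell, Monte Carlo SE about 1.1 points). The sponsor should confirm that CIP 8.2.3 does not already say this.

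The cost is two SAP sentences and one model option, with no new data. At a true rate ratio of 0.7 and no overdispersion, power beyond open label is 59.9-75.1% with Poisson and 60.1-75.2% with robust errors. At variance 1 it falls from 60.5-76.1% to 53.3-65.7%, but the higher figures belong to a test with a true error of 8.1-10.9%. On treatment the fall at variance 1 is 2-10 points.

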2.3.3 Descriptive Endpoints

Hemocompatibility Score: The Hemocompatibility Score (HCS) is a tiered hierachal score that weighs each hemocompatibility related adverse event by its escalating clinical relevance (1, 2). The HCS will be calculated for each subject in the mITT population and summarized for the treatment group as a median score and range.

Rehospitalizations: The rehospitalization rate will be calculated based on the number of subjects who require a rehospitalization (excluding the hospitalization for the implant), for any cause, after randomization and initiation of the study treatment (14 or more days post implant), divided by the number of subjects. Patient year of support will be the cumulative patient duration from 14 days post implant to outcome (transplant, explant, withdrawal or death) or until the last subject reaches their 12-month follow-up, whichever occurs first.

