5.8 Total Expected Duration of the Clinical Investigation

The expected duration of each subject's participation is at least 12 months and up to 36 months post-implant. Scheduled visits and data collection for this clinical investigation will occur at Baseline, Implant, Randomization, Week 1 \pm 3 days, Discharge, Month 1 \pm 7 days, Month 3 \pm 30, Month 6 \pm 30 days, Month 9 \pm 30 days, Month 12 \pm 30 days and, in patients still on the treatment arm medication, follow up will continue every 6 months \pm 60 days until the final ongoing patient completes their month 12 follow up visit. Subjects not on the treatment arm medication will be exited from the trial at the conclusion of their month 12 follow-up visit. The expected duration of enrollment is 24 months. Therefore, the total duration of the clinical investigation is expected to be 36 months.

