6.8.1 Continued follow up beyond 12-months post implant

Subjects on the treatment arm medication will be followed every six months after the 12-month follow up visit until the final ongoing subject reaches the 12 month visit or experiences a study outcome. Only treatment arm medication details, subject status (including death, withdrawal, or transplant) along with adverse events and device deficiencies will be collected along with additional supportive data should adverse events or device deficiencies occur. If a patient's clinical course after 12 months of follow up requires transition to open-label, the patient will be considered to have reached the end of study follow up unless the transition to open label is due to a stroke, in which case the patient should be followed for an additional 60-days to capture the MRS score. The clinical reason for transition to open-label will be captured. Subjects transitioned to open label prior to 12 months of follow up should be followed to their 12-month follow up.

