1.3 Clinical Investigation Design

This is a prospective, randomized, double-blinded, placebo-controlled clinical investigation of advanced heart failure patients treated with the HM3 with two different antithrombotic regimens: vitamin K antagonist with aspirin vs vitamin K antagonist with placebo. [REDACTED]

The clinical investigation has been designed to involve as little pain, discomfort, fear, and any other foreseeable risk as possible for subjects.

The clinical investigation will be conducted at up to 50 centers worldwide. The primary, and secondary endpoints will be evaluated as described in this SAP. Outcomes for this study include death, transplant, withdrawal or pump exchange. All subjects, site, Clinical Events Committee (CEC), and sponsor personnel, will remain blinded to the randomization scheme until the last ongoing study subject completes follow-up (specifically, experiences an outcome or reaches 12-months of follow up) and all data have been collected and adjudicated, exceptions will be justified in the study blinding plan (eg. DSMB). After a patient reaches 12-months of follow up, they will continue to be followed every 6-months, as long as they remain on the treatment arm medication, until the last ongoing patient reaches 12-months of follow up. Beginning at the 12-month follow-up visit, patients should be requisitioned two bottles of the treatment arm medication to cover the 6 months until the next follow up visit.

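### The rehospitalisation measure in SAP 2.3.3 is a proportion of subjects with no time limit, over follow-up whose length after month 12 depends on staying on study drug

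*SAP*

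**What the plan says.** **The formula (SAP 2.3.3).** "The rehospitalization rate will be calculated based on the number of subjects who require a rehospitalization", for any cause, leaving out the implant stay and starting at day 14. The denominator and the sentence after it read: "divided by the number of subjects. Patient year of support will be the cumulative patient duration". No end date is given for the count. The patient-years start at day 14 and stop at an outcome; the administrative stop is described as "until the last subject reaches their 12-month follow-up, whichever occurs first". No visible rehospitalisation formula uses that quantity.

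**The neighbouring endpoints (SAP 2.3.2).** Bleeding, stroke and pump thrombosis are counted as events, divided by years of support and compared by Poisson regression.

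**Follow-up.** Protocol 5.8: "The expected duration of each subject's participation is at least 12 months and up to 36 months post-implant". Past month 12, SAP 1.3 says of subjects that "they will continue to be followed every 6-months, as long as they remain on the treatment arm medication". Those off study drug leave at month 12 (Protocol 5.8 and 6.8). Those who move to open label after month 12 finish follow-up then, apart from 60 days for stroke scoring (Protocol 5.6).

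**What is collected after month 12.** Protocol 6.8.1: "Only treatment arm medication details, subject status (including death, withdrawal, or transplant) along with adverse events and device deficiencies will be collected", with supportive data if an adverse event or device deficiency occurs. Hospitalisations are not named. Protocol 6.9.3, however, captures all hospitalisations in every subject throughout follow-up. Table 2 lists them in its as-occurs column, and its footnote 8 extends associated as-occurs items past month 12.

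**The concern.** An ever/never proportion rises with the time a subject is observed. Here, time beyond month 12 is granted only to subjects still on study drug, so it is decided after randomisation. Moves to open label follow clinical events (Protocol 5.6), which the treatment itself may change. The arms can therefore differ in length of observation, and the proportion would mix that difference with any effect on rehospitalisation.

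SAP 1.4.3 presents this endpoint as showing change that results from removing antiplatelet therapy, so the two arms will be read against each other even without a test. The paragraph also begins one measure and defines the denominator of another, so two programmers could report different results from the same data.

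**Working it through.** **1. Spread of follow-up.** Protocol 5.8 gives 24 months of enrolment. Adding 12 months for the last subject gives 24 + 12 = 36 months, the plan's own figure. A subject who stays on drug is observed for 12 to 36 months, and one off drug by month 12 for 12 months.

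The documents give no expected rehospitalisation rate and no drug retention by arm. Both are assumed below.

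**2. Simple check, same hazard *h* in both arms.** Follow-up is 1 year for subjects who exit at month 12, otherwise 1 year plus a uniform 0 to 2 years.

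- Exit at month 12: P₁ = 1 − exp(−h)
- Stay on drug: P₂ = 1 − exp(−h) × [1 − exp(−2h)] / (2h)
- Gap between arms = (difference in exit share) × (P₂ − P₁)

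With assumed exit shares of 30% and 15%:

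- h = 0.6 per year: P₁ = 45.1%, P₂ = 68.0%; gap = 0.15 × 22.9 = 3.4 points
- h = 1.0 per year: P₁ = 63.2%, P₂ = 84.1%; gap = 0.15 × 20.9 = 3.1 points

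**3. Fuller check.** This is a simulation with 1,000,000 subjects per arm, uniform enrolment over 24 months, exponential time to stopping drug, exit as the protocol describes, counting from day 14, and an identical constant hazard in both arms. The assumed 12-month rehospitalisation risk is 30% to 80%, and the assumed share with a terminating outcome by month 12 is 0 or 25%. The 79% retention value is anchored on the earlier HM3 trial, where 78/371 = 21% were without aspirin at 1 year (Protocol 1.1.1). The other retention values are illustrative.

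| On drug at month 12, arm A / arm B | Gap in crude proportion, A − B |
|---|---|
| 79% / 79% | 0 (within 0.1 point of simulation error) |
| 85% / 75% | 1.3 to 3.1 points |
| 79% / 60% | 2.2 to 5.4 points |
| 90% / 60% | 3.6 to 8.9 points |

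**4. One case in full.** 12-month risk 50% (hazard ln 2 = 0.69 per year), retention 79% / 60%, no terminating outcomes:

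| Measure | Arm A | Arm B |
|---|---|---|
| Subjects ÷ subjects, no time limit (SAP 2.3.3) | 65.1% | 59.7% |
| Proportion from day 14 to month 12 | 48.6% | 48.7% |
| Events per observed patient-year | 0.69 | 0.69 |
| Events per patient-year as SAP 2.3.3 defines it | 0.58 | 0.50 |

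The second and third measures remove the false difference.

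**5. Why the fourth does not.** Mean observed time from day 14 is 1.64 and 1.40 years. The SAP definition runs to an outcome or to study close: 2 − 14/365 = 1.96 years in both arms. So 0.69 × 1.64/1.96 = 0.58, and 0.69 × 1.40/1.96 = 0.50 after rounding. Exit off drug at month 12, or at open-label transition later, is not a named stop, so time in which nobody was observing enters the denominator. It could be treated as withdrawal, but Protocol 5.6 and 6.8 describe these subjects as having completed the study.

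**The case against.** The strongest reply is that this is an incompletely worded per-patient-year rate. The definition directly follows the word rate, it echoes the years of support used in SAP 2.3.2, and parts of the SAP are redacted. That may well be the intent. But no such rate is written in the visible text, and step 5 shows that the definition would still need a stop at actual exit.

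It is also fair that the double-blind design may keep retention similar, in which case the gap is zero. Outcomes such as death and transplant shrink it too: with 25% by month 12, the case in step 4 falls from 5.4 to 3.5 points. And the endpoint is descriptive, with no test and no part in the success criterion (SAP 2.6).

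Three stronger readings are tempting, and the documents do not support them:

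- *One arm will look worse.* This needs a retention difference between arms, on which the documents are silent.
- *The rate will be greatly understated because hospitalisations stop being recorded at month 12 while patient-years run on.* This needs a rate that the SAP does not specify, and Protocol 6.9.3 and Table 2 footnote 8 point to continued capture. It is also the opposite of the premise in steps 2 to 4: if nothing were counted after month 12, the retention effect would disappear.
- *The economic endpoint inherits the problem.* The visible SAP gives no method for that endpoint, so no dependence can be shown.

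**Conclusion.** The point holds in conditional form. As written, SAP 2.3.3 yields a proportion with no time limit over follow-up that depends on drug retention. Given unequal retention and counting of hospitalisations after month 12, it shows a false excess in the arm that stays on drug longer: about 1 to 9 points across the assumed scenarios, and none with equal retention. The size rests on assumed hazards, retention and outcome rates, with a constant hazard that is equal in both arms. Using the patient-years as defined would leave a distortion in the same direction.

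The primary conclusion is unaffected. The change is still worth making before unblinding, because it removes a bias from a named endpoint at little cost.

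**What to change.** In SAP 2.3.3, replace the rehospitalisation paragraph with two measures by arm:

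1. The proportion with at least one rehospitalisation from day 14 to 1 year post implant. Protocol 5.6 keeps subjects who go open label before month 12 in follow-up to month 12 where possible, so this window is largely free of the retention effect. Visit windows allow a month-12 exit as early as day 12 × 30 − 30 = 330, so state how exits shortly before 1 year are handled, for example by a cumulative incidence estimate with death and transplant as competing events.
2. Rehospitalisation events divided by observed patient-years, with events and exposure over the same window: either to 1 year or to each subject's actual exit. Name exit off drug at month 12, and open-label transition after month 12, as stops.

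Reconcile the restricted list in Protocol 6.8.1 with Protocol 6.9.3 and Table 2 footnote 8, so that it is clear whether hospitalisations are collected after month 12. Use later time only if they are.

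Cost: SAP wording and one protocol clarification; no new data. The drawback of a 1-year window is that it sets aside later data. Running the second measure to actual exit keeps them.
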